Research Monitor/Independent Safety Monitor	[name], MS, FACP, FCCP Center for Vaccine Development University of Maryland School of Medicine [name] [contact] [contact] E-mail: [contact]

PSSO^a SAEs will be forwarded to the DMID Pharmacovigilance Group by the USAMRDC ORA PSSO in accordance with the Safety Management Plan.

Table 7: SAE Information to Be Reported to the USAMRDC ORA PSSO

Notification Method	Information to Be Provided
E-mail or Telephone (within 24 hours of site awareness)	IND number, sponsor study number, name of the investigational product, and investigator name and contact number
	Subject identification number
AND	
E-mail or Fax	Cover sheet or letter
	Adverse event case report form
	Serious adverse event report form
	Concomitant medication case report form or a list of concomitant medications
	Medical record progress notes including pertinent laboratory/diagnostic test results

NOTE: When submitting SAE reports via e-mail, the subject line of each email notification will read as follows:

SAFETY REPORT – IND # _____, Sponsor Study # _____, Subject# _____, Event Term: _____

In order to comply with regulations mandating sponsor notification of specified SAEs to the FDA within 7 calendar days, investigators must submit additional information as soon as it is available. The sponsor's representative will report unexpected SAEs associated with the use of the product to the FDA as specified at 21 CFR 312.32 (c).

Investigators must follow all relevant regulatory requirements as well as specific policy regarding the timely reporting of SAEs to the RM/ISM, USAMRDC ORA PSSO, and the UMB IRB.

Reporting to the USAMRDC ORA PSSO does not fulfill the investigator's duty to report all unanticipated problems involving risk to subjects or others (UPIRTSOs) to the IRB. The PI will notify the UMB IRB, DMID, and the RM/ISM.

10.7.1.2. Reporting to the IRB

UPIRTSOs, SAEs related to participation in the study, and all subject deaths related to participation in the study should be promptly reported within 24 hours of site awareness by telephone, email, or fax to the UMB IRB. A complete written report should follow the initial notification.

Investigators are required to forward safety information provided by the sponsor's representative to the IRB.

All UPIRTSOs must be promptly reported to the USAMRDC ORP HRPO.

10.7.2. Reporting Additional Immediately Reportable Events to the USAMRDC ORA PSSO, UMB IRB, DMID, and the USAMRDC ORP HRPO

10.7.2.1. Pregnancy

Each pregnancy must be reported immediately using the Pregnancy Report Form (**within 24 hours of identification**) by e-mail or fax to the USAMRDC ORA PSSO. Report the incident to UMB IRB in accordance with IRB policy. USAMRDC ORA PSSO will be responsible for notifying DMID within 48 hours of notification by site.

Subjects who become pregnant after Day 0 will be followed until 30 days after delivery to determine outcome, including spontaneous or voluntary termination, details of the birth, and the presence or absence of any birth defects, congenital abnormalities, or maternal and/or newborn complications. The following information will be gathered for outcome, date of delivery, health status of the mother and child including the child's gender, height and weight. Complications and or abnormalities should be reported including any premature terminations. While pregnancy is not per se an AE/SAE, the product of the pregnancy could potentially be an AE/SAE. A pregnancy is reported as an AE or SAE only when there is suspicion that the investigational product may have interfered with the effectiveness of contraception or there was a serious complication in the pregnancy including a spontaneous abortion, an elective termination for medical rationale, or the infant has a congenital anomaly/birth defect.

Follow-up information should be e-mailed to [contact], using the Pregnancy Report Form stating that this is a trimester update or final report to the previously reported Pregnancy Report and giving the date of the original report.

10.7.2.2. AE-related Withdrawal of Consent

Any AE-related withdrawal of consent during the study must be reported *immediately* (**within 72 hours of identification**) by e-mail or fax to the sponsor's representative. USAMRDC ORA will be responsible for notifying DMID within 48 hours of notification by site.

10.7.2.3. Pending Inspections/Issuance of Reports/Serious or Continuing Noncompliance/Suspensions, Clinical Holds, or Terminations/Subject Becomes a Prisoner

The knowledge of any pending compliance inspection/visit by the FDA, Office for Human Research Protections (Department of Health and Human Services), or other government agency concerning clinical investigation or research, the issuance of Inspection Reports, Form FDA 483, warning letters, or actions taken by any regulatory agency including legal or medical actions and any instances of serious or continuing noncompliance with the regulations or requirements will be reported by the principal investigator immediately to the UMB IRB, and the sponsor's representative. USAMRDC ORA will be responsible for notifying ORP HRPO, DMID and Geneva within 24 hours of notification by site. Additionally, all suspensions, clinical holds (voluntary or involuntary), or terminations of this research by the IRB, the institution, the sponsor, or regulatory agencies must be reported to the USAMRDC ORP HRPO, DMID and Geneva.

Change in subject status when a previously enrolled human subject becomes a prisoner must be promptly reported to the USAMRDC ORP HRPO. The report must include actions taken by the institution and the IRB.

10.7.3. IND Annual Report to the FDA

The PI will be responsible for the preparation of a detailed annual synopsis of clinical activity, including adverse events, for submission to the sponsor's representative (USAMRDC). Each annual report will summarize IND activity for 1 year beginning approximately 3 months before the IND FDA anniversary date. The sponsor's representative will notify the PI of the due date with sufficient time for the PI to assemble the required information.

10.7.4. Final Report

A final study report will be prepared in accordance with "Guidance for Industry: Submission of Abbreviated Reports and Synopses in Support of Marketing Applications" and ICH E3 Guideline "Structure and Content of Clinical Study Reports" and provided to the sponsor's representative for review and approval. The sponsor's representative will use this report to prepare the final clinical study report for submission to the FDA.

The PI will report all AEs to the sponsor (USAMRDC ORA) and the UMB IRB in the appropriate safety, annual, and/or final reports. After appropriate data cleaning and query resolution between the clinical site, sponsor's clinical monitor, and clinical data manager, SAEs from the clinical database will be reconciled with the sponsor's SAE database. SAEs and AEs for inclusion in annual and final reports to the FDA will be provided from the clinical database by the clinical data manager at the UMB CVD.

The final study report submitted to the IRB, including a copy of any acknowledgement documentation and any supporting documents, will be submitted to the HRPO as soon as all documents become available.

11. STATISTICS

Detailed statistical procedures, listings, table shells and figures will be provided in a separate statistical analysis plan (SAP) written shortly after protocol approval but before any subject enrollment. The SAP will be finalized before study close-out and database lock. The following key statistical components will be considered and a detailed description will be documented in the SAP:

- Primary, secondary, and exploratory endpoints and how they will be measured,
- Statistical methods and tests that will be used to analyze the endpoints,
- Strategy that will be used if the statistical test assumptions are not satisfied,
- Indication of whether the comparisons will be one-tailed or two-tailed (with justification of the choice) and the level of significance to be used,
- Identification of whether any adjustments to the significance level or the overall p value will be made to account for any planned or unplanned subgroup analyses or multiple testing,
- Specification of potential adjusted analyses and a statement with which covariates or factors will be included,
- Planned exploratory analyses and justification of their importance, and
- Any subgroup effects with biological justification and support from within and outside the study.

11.1. Description of Statistical Methods

Descriptive analysis of safety and reactogenicity outcomes will include all subjects who meet the eligibility criteria, receive at least one vaccination, and for whom safety data are available. Summary tables will be created in which incidence, severity, and relationship to the use of investigational product of individual solicited local and systemic signs, symptoms, or trending unsolicited events are delineated by study group, severity, gender, and overall. Unsolicited AEs and SAEs will be analyzed in a similar fashion.

Descriptive analysis of immunogenicity outcomes will include all subjects who meet the eligibility criteria, receive at least one vaccination, and for whom serological data are available. The primary analysis variable will be the proportion of seropositive subjects (defined as $\text{PsVNA50} \geq 1:20$) at each scheduled time point for which blood samples are taken (eg, Days 0, 28, 56, 84 and 140), and the final overall rate of seroconversion over all scheduled time points to study completion for each study group. Seroconversion is defined as a post-vaccination HTNV- or PUUV-specific titer of $\geq 1:40$, or a minimum four-fold rise compared to baseline titer and all study volunteers will begin the study with a baseline titer < 20 (ie, seronegative). For each study group, a binomial proportion and 95% confidence interval (CI) will be calculated. The secondary analysis variable will be geometric mean titers (GMT), with 95% CIs, of the PsVNA50 for HTNV- and PUUV-specific antibodies at each scheduled time point for which blood samples are taken for each study group and over all time points for each study group. GMT, standard errors, and 95% CIs will be calculated using log-transformed titers. For titers below the lower limit of detection (< 20), the value will be transformed to a value equal to the lower limit of detection (ie,

20) divided by the square root of 2, which equals 14.1. Exploratory objectives may evaluate PsVNA80 titers, which may be calculated for informational purposes, and may evaluate PsVNA50 titers against related Seoul and Dobrava viruses.

For hematology and serum chemistry tests, any clinically significant changes from baseline value will be identified. The median, interquartile range, and normal values for each laboratory value (as determined by the contract laboratory) will be reported for each treatment group for each specimen collection point.

11.1.1. Safety Analyses

Adverse events will be classified by MedDRA system organ class and preferred term, severity, and relationship to study treatment. Serious adverse events will be described. A complete listing of adverse events for each subject will provide details including severity, relationship to study product, onset, duration, and outcome. Laboratory results will be summarized by laboratory parameter, severity, study day, and study arm.

Safety analysis will include data collected from all subjects. Adverse event data will be listed individually (including intervention and outcome) and summarized by body system and preferred terms within a body system for each treatment group. Serious and/or unexpected AEs will also be discussed on a case-by-case basis. For the tabulation of the AEs by body system, a subject will be counted only once in a given body system. For example, a subject reporting nausea and diarrhea will be reported as one subject, but the symptoms will be listed as 2 separate AEs within the class. Therefore the total number of AEs reported within a body system may exceed the number of subjects within the body system reporting AEs.

The total number of AEs reported within body systems between each treatment group will be compared using Fisher's exact test.

Changes in pulse rate, systolic and diastolic blood pressure, weight, and respiratory rate will be compared within each group and among groups using analysis of variance procedures.

Depending upon the sample size, the more common adverse events that may be drug related should be examined for a dose, duration, or demographic relationship, or using other analyses such as standard life-table methods.

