4.4.2.1.2. Safety Results

During the performance of the TDS-IM V1.0 study, there were no significant safety concerns involving the investigational products. Overall, 30/31 (96.8%) subjects receiving at least 1 dose of HTNV DNA, PUUV DNA, or HTNV/PUUV DNA vaccines reported at least 1 AE. Of the 246 AEs reported, 96.7% were graded as mild to moderate. Seven out of 8 AEs identified as either Grade 3 or Grade 4 were considered unrelated to the study vaccine; 1 Grade 3 AE was considered unlikely to be related. There were 2 SAEs reported during this study, both involving transient Grade 4 laboratory abnormalities detected in otherwise asymptomatic individuals (hypoglycemia and hyperkalemia, respectively). Each event was evaluated and determined to be unrelated to study participation.

Seventy-six incidents of injection site pain were reported in 28/31 (90.3%) subjects, accounting for 30.9% of all AEs. The other most commonly reported AEs were headache (5.7%), injection site bruising (3.7%), muscle aches (3.3%), and fatigue (3.3%). Ninety-six/246 (39.0%) AEs were

considered related to injection, of which 87 (90.6%) were local reactions at the injection site (pain, bruising, or erythema).

4.4.2.2. A Phase I, Randomized, Observer-blind, Placebo Controlled Study to Assess the Safety, Reactogenicity, and Immunogenicity of a Venezuelan Equine Encephalitis DNA Vaccine Candidate Administered Intramuscularly or Intradermally by Electroporation to Healthy Adults (NCT01984983)

In a Phase 1, randomized, double-blind, placebo-controlled study, a DNA-based Venezuelan Equine Encephalitis vaccine, pWRG/VEE, or placebo control was administered to 41 healthy, adult subjects using either the Ichor TDS-IM V1.0 or TDS-ID EP devices ([Hannaman, et al, 2016](#)). Subjects received up to 3 administrations of the pWRG/VEEV vaccine. Subjects in the TDS-IM V1.0 groups received 0.5 mg (N = 8) or 2.0 mg (N = 9) of pWRG/VEE or a saline placebo (N = 4) in a 1.0-mL injection. Subjects in the TDS-ID groups received 0.08 mg (N = 8) or 0.3 mg (N = 8) of pWRG/VEE or a saline placebo (N = 4) in a 0.15-mL injection. Subjects were monitored for a total of 360 days.

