6.3. Measures Taken to Minimize/Avoid Bias

6.3.1. Randomization

A randomization plan will be used to allocate subjects into experimental groups, per the study priorities described in Section 6.2. In addition, as of Version 5.0, ten replacement subjects will be enrolled into Group 6. A fixed random allocation will ensure that the groups are balanced in size at the end of experiment.

Designated study personnel (excluding the principal investigator [PI] and other investigators) will fill the vaccine cohorts as potential subjects successfully complete the screening process and are deemed eligible to participate by the PI (or another designated investigator). For the purposes of this study, the groups will be defined as follows, and each subject will receive one dose of vaccine on Days 0, 28, and 56.

Group 1 (12 subjects): HTNV by ID EP

Group 2 (12 subjects): HTNV by IM EP

Group 3 (12 subjects): PUUV by ID EP

Group 4 (12 subjects): PUUV by IM EP

Group 5 (12 subjects): HTNV/PUUV by ID EP

Group 6 (22 subjects): HTNV/PUUV by IM EP

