11.3. Level of Significance to Be Used

All statistical analyses will be made using a two-tailed $\alpha = 0.05$.

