TABLE 3.1: Proportion of Seropositive Subjects at Each Blood Collection Time Point

Collection Point	Group 1 (N=X)		Group 2 (N=X)		Group 3 (N=X)		Group 4 (N=X)		Group 5 (N=X)		Group 6 (N=X)	
	n	%	n	%	n	%	n	%	n	%	n	%
1	x	xx										
	[x,x]		[x,x]		[x,x]		[x,x]		[x,x]		[x,x]	
2												
3												
4												
5												
6												
7												

Note: 95% confidence intervals for sample proportion in brackets

TABLE 3.2: Proportion of Subjects that Ever Seroconverted at Each Blood Collection Time Point

Collection Point	Group 1 (N=X)		Group 2 (N=X)		Group 3 (N=X)		Group 4 (N=X)		Group 5 (N=X)		Group 6 (N=X)	
	n	%	n	%	n	%	n	%	n	%	n	%
1	x	xx										
	[x,x]		[x,x]		[x,x]		[x,x]		[x,x]		[x,x]	
2												
3												
4												
5												
6												
7												

Note: 95% confidence intervals for sample proportion in brackets

TABLE 3.3: Duration of Seropositivity if Ever Seroconverted

	Group 1 (n=x)	Group 2 (n=x)	Group 3 (n=x)	Group 4 (n=x)	Group 5 (n=x)	Group 6 (n=x)
Mean						
Standard Deviation						
95% CI for Mean						
1st Quartile						
Median						
3rd Quartile						
Min						
Max						

TABLE 3.4: Geometric Mean Titers of the PsVNA50 at Each Blood Collection Time Point

Collection Point	Group 1 (N=X)		Group 2 (N=X)		Group 3 (N=X)		Group 4 (N=X)		Group 5 (N=X)		Group 6 (N=X)	
	μ	SD										
1	x	x	x	x	x	x	x	x	x	x	x	x
	[x,x]		[x,x]		[x,x]		[x,x]		[x,x]		[x,x]	
2												
3												
4												
5												
6												
7												

Note:

- μ = mean; SD = standard deviation
- 95% confidence intervals for sample proportion in brackets

TABLE 4.1: Safety Analysis Group Comparison: Ever Experienced Solicited Adverse Events

Group:	1	2	3	4	5	6	P-value ¹
N=	x	x	x	x	x	x	
% Reporting	xx	xx	xx	xx	xx	xx	
(95% CI)	(x,x)	(x,x)	(x,x)	(x,x)	(x,x)	(x,x)	
Pair 1	•	•					x
Pair 2		•	•				x
Pair 3				•	•		x
Pair 4	•				•		x
Pair 5		•			•		x
Pair 6		•				•	x
Pair 7			•		•		x

¹P-value obtained from a two-sided Fisher's exact test

TABLE 4.2: Safety Analysis Group Comparison: Ever Experienced Unsolicited Adverse Events

Group:	1	2	3	4	5	6	P-value ¹
N=	x	x	x	x	x	x	
% Reporting (95% CI)	xx (x,x)	xx (x,x)	xx (x,x)	xx (x,x)	xx (x,x)	xx (x,x)	x
Pair 1	•	•					x
Pair 2		•	•				x
Pair 3				•	•		x
Pair 4	•			•			x
Pair 5		•		•			x
Pair 6	•				•		x
Pair 7			•		•		x

¹P-value obtained from a two-sided Fisher's exact test

TABLE 4.3: Immunogenicity Analysis: Ever Seroconverted

Group:	1	2	3	4	5	6	P-value ¹
N=	x	x	x	x	x	x	

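### Protocol 11.1.1 applies Fisher's exact test to total AE counts by body system, which is not valid as written; the SAP's Fisher tables count subjects, and the two documents are not reconciled

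*Protocol*

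**What the plan says.** Protocol 11.1.1 sets two counting rules and then a test. For the body-system tabulation, "a subject will be counted only once in a given body system". A subject with nausea and diarrhea is one subject but two AEs, and the section concludes: "Therefore the total number of AEs reported within a body system may exceed the number of subjects within the body system reporting AEs". The next sentence is: "The total number of AEs reported within body systems between each treatment group will be compared using" Fisher's exact test. Protocol 11.3 sets a two-tailed 5% level for all analyses.

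SAP section 8 repeats the counting rules almost word for word but not the Fisher sentence. It points instead to Tables 4.1 and 4.2. The first of these shells is titled "TABLE 4.1: Safety Analysis Group Comparison: Ever Experienced Solicited Adverse Events"; the second is the same for unsolicited AEs. Both apply a two-sided Fisher test to the percentage of subjects reporting, and neither is split by body system. SAP Tables 2.3.3 and 2.3.4 do split unexpected AEs by system organ class, as numbers and percentages of subjects, without p-values. Event totals appear only in Table 2.2, which has no group columns and no p-value.

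**The concern.** Fisher's exact test needs independent units and a fixed denominator for each group. A count of AEs supplies neither. Three doses per subject mean that one reactive person can contribute several events to the same body system, and the test treats them as if they came from different people. If reactions cluster within subjects, the p-value is too small and a difference between groups can be declared on the strength of one or two individuals. SAP 6.7 plans no multiplicity adjustment, so any excess error would recur across body systems and pairs of groups. Safety is the trial's primary objective.

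The protocol also leaves the analyst to invent the denominator: subjects, subject-doses or all AEs in the group. Each choice gives a different test.

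**Working it through.** **The plan's own figure.** The documents give none for this comparison beyond the two-tailed 5% level.

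**Inputs from the documents.** 12 subjects in each of Groups 1 to 5 and 22 in Group 6 (Protocol 6.3.1); three injections each (Protocol 6.2). In the earlier trial of these vaccines by intramuscular electroporation there were 246 AEs in 31 subjects, and "Seventy-six incidents of injection site pain were reported in 28/31 (90.3%) subjects" (Protocol 4.4.2.1.2). Doses in that trial: 27×3 + 2×2 + 2×1 = 87 (Protocol 4.4.2.1).

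**Step 1: subjects as denominator.** AEs per subject in the earlier trial: 246/31 = 7.9 over all body systems. If 12 subjects have, say, 15 AEs in one body system, the second cell is 12 − 15 = −3 and the test does not exist.

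**Step 2: subject-doses as denominator (assumption).** 12×3 = 36 per group. Suppose two subjects in one group have an AE after every dose and nobody in the other group has any.
- By events: 6/36 v 0/36, p = 0.025.
- By subjects: 2/12 v 0/12, p = 0.48.

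**Step 3: error rate with no true difference.** Assumptions: at most one event per subject-dose in the body system; events over the three doses beta-binomial with per-dose rate π and within-subject correlation ρ. Each subject's count has parameters a = π(1−ρ)/ρ and b = (1−π)(1−ρ)/ρ (plain binomial at ρ = 0). The group total is the sum over subjects. The error rate is the total probability of all pairs of group totals with two-sided Fisher p ≤ 0.05, by full enumeration. The documents give no value for ρ, so a range is shown.

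Event-level rejection, 12 v 12:

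| π per dose | ρ = 0 | 0.1 | 0.3 | 0.5 | 0.7 |
|---|---|---|---|---|---|
| 0.05 | 0.3% | 0.7% | 1.9% | 3.5% | 5.8% |
| 0.10 | 1.4% | 2.4% | 5.1% | 8.2% | 11.8% |
| 0.20 | 2.6% | 4.2% | 7.9% | 11.8% | 15.7% |
| 0.30 | 2.8% | 4.5% | 8.3% | 12.3% | 16.1% |
| 0.50 | 2.5% | 4.1% | 7.8% | 11.7% | 15.5% |

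The subject-level Fisher test on the same data (at least one event, yes or no) rejects at most 2.3% in every cell.

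For 12 v 22, at π of 0.2 to 0.5, event-level rejection is about 10% to 19% for ρ of 0.3 to 0.7 and about 6% at ρ = 0.1; subject-level stays below 3%.

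**Step 4: is clustering plausible?** Pain rate per dose: 76/87 = 0.874, assuming at most one incident per dose. Under independence the expected number of subjects with no pain is 27×0.126³ + 2×0.126² + 2×0.126 = 0.34. Three of 31 had none; the probability of three or more is 0.002. The ρ that makes the expected number equal 3 is about 0.8. At that rate and ρ, event-level rejection is 15.8% for 12 v 12, against 0.2% by subjects. This is one symptom in 31 people, so it is a rough guide only.

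**The case against.** The strongest reply is that the SAP is where tests are specified (Protocol section 11 says so) and that it plans no event-level test. No table shell would carry the disputed p-value. The comparison is also exploratory: Protocol 11.2 says the trial is not designed to show significant group differences, SAP section 5 calls all analyses exploratory, the halting rules count subjects, and Protocol 11.4 sets no statistical criteria for termination. This stands, and it limits the reach of the point. It does not remove it. The SAP presents itself as elaborating the protocol's outline and nowhere withdraws the sentence. Protocol 11.6 requires departures from the protocol's statistical plan to be described in an amendment to both documents, and neither describes this one. The SAP is dated January 2019, and the later Version 6.0 protocol still carries the sentence.

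A second reply is that the size depends on choices the protocol does not make. That is also right. With 12 per group the inflation vanishes when correlation is 0 to 0.1, and for rare events it is absent or slight.

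A reader might infer from 76/28 = 2.7 pain events per affected subject that clustering is proven. It is not: when nearly everyone has pain after each of three doses, the ratio approaches 3 even under independence. The evidence for clustering is the number of subjects without pain (step 4).

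**Conclusion.** The sentence in Protocol 11.1.1 is wrong as written: it tests non-independent events with no stated denominator. That conclusion needs no simulation. The size does rest on assumptions: a subject-dose denominator, at most one event per dose in a body system, and the chosen rates and correlations. With 12 v 12 these give about 8% to 16% rejection at nominal 5% for rates of 0.2 to 0.5 and correlation 0.3 to 0.7, under 5% at correlation 0 to 0.1, and 2% to 6% at a rate of 0.05 with correlation 0.3 to 0.7. The subject-level test stays below 2.5%.

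A reader might go further and infer that the reported safety comparisons will over-call group differences, or that the primary safety analysis is invalid. The documents do not support either. The primary analysis is descriptive, and the SAP's planned Fisher tests on AEs are on subjects. What exists is an unreconciled conflict between protocol and SAP over an exploratory comparison, which does harm only if the protocol sentence is followed.

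**What to change.** Amend the sentence in Protocol 11.1.1 to say that the number of subjects with at least one AE in each body system will be compared between groups by Fisher's exact test, and that total event counts will be reported descriptively without p-values. Add the same statement to SAP section 8, which has no such line now; Tables 4.1 and 4.2 do not supply it because they are not by body system. The cost is one sentence in each document. No new data, visits or subjects are needed, and the counting rule already in both documents supplies the numerator.
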